14.6.3 Malignancies including lymphoma

Malignancies will be presented in 2 separate tables based on the following SMQs:

- Malignant or unspecified tumours
- Malignant tumours

Events included in the ‘Malignant tumours’ tabulation will be a subset of the events in the ‘Malignant or unspecified tumours’ tabulation. The SMQ search should include all TEAEs which code to a PT included in the Scope=Narrow group within each SMQ.

The output tables will include 2 different overall incidence rows:

- The first overall incidence row will summarize ‘Any malignancies (including unspecified)’ or ‘Any malignancies’ (depending on the table) and this row will summarize the incidence of all AEs flagged for inclusion in the table, regardless of the HLT it codes to.
- The second overall incidence row will summarize ‘Any malignancy (including unspecified, excluding non-melanomic skin cancers)’ or ‘Any malignancy (excluding non-melanomic skin cancers)’ (depending on the table) and this row will summarize the incidence of AEs flagged for inclusion in the table, excluding those which code to an HLT of ‘skin neoplasms malignant and unspecified (excl melanoma)’.

14.6.4 Cytopenias

Cytopenias will be tabulated separately based on the SMQ = ‘Haematopoietic cytopenias’. The SMQ search should include all TEAEs that code to a PT included in the Scope=Broad and/or Scope=Narrow groups within the SMQ.

14.6.5 Neuropsychiatric events

Neuropsychiatric events (in particular depression, anxiety and suicide ideation or behavior) will be tabulated separately based on the SMQ = ‘Depression and suicide/self-injury’. The SMQ search should include all TEAEs which code to a PT included in the Scope=Broad and/or Scope=Narrow groups within the SMQ.

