#### **12.1.3 Adverse events for special monitoring**

UCB has identified AEs for special monitoring (AESM). An AESM is an AE or safety topic for which special monitoring, additional data collection activities, and/or enhanced signal detection activities (within UCB), are considered appropriate. Identified AESM can be of particular interest based on findings from the IMP clinical program to date, potential risks generally associated with biologic immunomodulators, or comorbidities and risk factors prevalent in the study population.

Adverse events for special monitoring for this study include: serious infections (including opportunistic infections and TB, see [Section 12.6.1](#)), cytopenias, hypersensitivities, suicide ideation or behavior (assessed using the C-SSRS), depression and anxiety (assessed using the

HADS, see [Section 9.4](#) ), major cardiovascular events and liver function test changes/enzyme elevations (ALT, AST, and bilirubin; see [Section 12.5.1](#)), and malignancies and inflammatory bowel diseases.

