8.3.4 Hospital Anxiety and Depression Scale

The HADS scores for anxiety (HADS-A) and depression (HADS-D) each range from 0 to 21 with higher scores indicating worse state. A score below 8 is considered to be normal whereas a score of 15 and above is considered severe (Snaith and Zigmond, 1994). The individual items, associated item scores and calculation rules for the anxiety and depression domains are provided in [Section 14.2](#).

The results of the HADS will be listed by subject and visit including the individual item responses and the derived domain scores for anxiety (HADS-A) and depression (HADS-D). Changes from Baseline will be calculated based on the domain scores only, and will be included in the listing.

Descriptive statistics will be presented by treatment group and visit for both absolute values and changes from Baseline, separately for each domain (HADS-A and HADS-D). The number and percentage of subjects with scores <8 for the HADS-A and HADS-D will be summarized by treatment group at each visit. The percentages will be based on the number of available observations at each visit; the number of subjects with missing data (including subjects who enroll in the extension study) will be included in the tabulation.

There will be no imputation of missing data for the HADS scores, either for the descriptive statistics or frequency tables.

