11.2.3 Presentation of adverse events

An overview of the number and percentage of subjects who experience TEAEs will be presented by treatment group (including All Subjects), based on the SS. This tabulation will include the number and percentage of subjects with any TEAEs, serious TEAEs, related TEAEs, discontinuation due to TEAEs, severe TEAEs, AEs leading to death and TEAEs leading to death; event counts will also be included. The tabulation will be repeated for Treatment Period TEAEs and Overall TEAEs.

In addition, the following summaries will be presented by treatment group (including All Subjects), SOC, high level term (HLT) and PT, based on the SS:

- Incidence of TEAEs during Treatment Period
- Incidence of TEAEs Overall
- Incidence of serious TEAEs during Treatment Period
- Incidence of serious TEAEs Overall

-
- Incidence of non-serious TEAEs during Treatment Period
 - Incidence of non-serious TEAEs Overall
 - Incidence of TEAEs during Treatment Period by relationship
 - Incidence of TEAEs Overall by relationship
 - Incidence of TEAEs during Treatment Period by maximum relationship
 - Incidence of TEAEs Overall by maximum relationship
 - Incidence of TEAEs during Treatment Period by maximum intensity
 - Incidence of TEAEs Overall by maximum intensity
 - Incidence of fatal TEAEs during Treatment Period by relationship
 - Incidence of fatal TEAEs Overall by relationship
 - Incidence of non-serious TEAEs during Treatment Period by relationship
 - Incidence of non-serious TEAEs Overall by relationship
 - Incidence of serious TEAEs during Treatment Period by relationship
 - Incidence of serious TEAEs Overall by relationship
 - Incidence of non-serious TEAEs during Treatment Period above threshold of 5% of subjects
 - Incidence of non-serious TEAEs Overall above threshold of 5% of subjects
 - Incidence of non-serious TEAEs during Treatment Period above threshold of 5% of subjects by relationship
 - Incidence of non-serious TEAEs Overall above threshold of 5% of subjects by relationship
 - Incidence of TEAEs during Treatment Period by SOC and PT (including the number and percentage of subjects and individual subject numbers/reported terms for each PT stratified by intensity, relationship and seriousness)
 - Incidence of TEAEs (including all TEAEs during Treatment and Post-Treatment Periods) by SOC, HLT and PT and including the EAIR and EAER calculated as described in [Section 11.2.2](#)

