 - Incidence of TEAEs (including all TEAEs during Treatment and Post-Treatment Periods) by SOC, HLT and PT and including the EAIR and EAER, stratified by overall ADA status (positive/negative)

In addition, separate AE summaries by treatment group, SOC, HLT and PT (including all TEAEs during Treatment and Post-Treatment Periods combined) will be included for the following AEs of special monitoring (AESM):

- Major cardiovascular events
- Serious infections, including opportunistic infections and tuberculosis (TB)
- Malignancies including lymphoma

- Cytopenias
- Neuropsychiatric events (in particular, depression and suicide)
- Inflammatory bowel disease
- Anaphylactic reaction (hypersensitivity and anaphylactic reactions)
- Hepatic events and drug-induced liver injury

All summary tables (including those for AESM) will contain the number and percentage of subjects and the number of events where applicable. A subject who has multiple events in the same SOC, HLT and PT will be counted only once in the subject counts but all events will be included. In addition, for all tabulations of AESM, the EAER and EAIR will be reported.

The criteria for identifying AESM and additional criteria for reporting AESM are provided in [Section 14.6](#).

In summaries including relationship to IMP, the following relationship categories will be included:

- Related
- Not related

Subjects who experience the same event multiple times will be included in the most related category for tabulations by maximum relationship. Events with missing relationship will be considered as 'Related' for summary purposes but shown as missing in the data listings.

In summaries including intensity, the following categories will be summarized:

- Mild
- Moderate
- Severe

Subjects who experience the same event multiple times will be included in the most severe category for tabulations by maximum intensity. Events with missing intensity will be considered as severe for summary purposes. All data will be presented as recorded in the database for the listings.

Adverse event summaries will be ordered by alphabetical SOC, alphabetical HLT within SOC and decreasing frequency of PT in the 'BKZ 320mg' (Treatment arm B) column for tables including event counts. For tables including only number and percentage of subjects, summaries will be ordered by alphabetical SOC, alphabetical HLT within SOC and decreasing incidence of PT within HLT and SOC in the 'BKZ 320mg' (Treatment arm B) column.

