11.4.4.3 C-SSRS

The results of the C-SSRS will be listed for each subject and visit.

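### The SAP's neuropsychiatric special-monitoring table names anxiety but gives no anxiety search, and no planned summary counts subjects who reach the protocol's C-SSRS or HADS-D action thresholds

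*SAP*

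**What the plan says.** Protocol 12.1.3 lists among the adverse events for special monitoring "suicide ideation or behavior (assessed using the C-SSRS), depression and anxiety (assessed using the" HADS). It thus names three topics and the instrument for each.

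SAP 14.6.5 repeats that scope: "Neuropsychiatric events (in particular depression, anxiety and suicide ideation or behavior) will be tabulated separately based on the SMQ" titled Depression and suicide/self-injury. It adds: "The SMQ search should include all TEAEs which code to a PT included in the Scope=Broad and/or Scope=Narrow groups within the SMQ". Nothing else feeds the table. The topic lists in SAP 11.2.3 and 14.6 describe the same topic more narrowly, as "Neuropsychiatric events (in particular, depression and suicide", without anxiety.

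The instruments are handled elsewhere. For the C-SSRS, SAP 11.4.4.3 says only: "The results of the C-SSRS will be listed for each subject and visit". HADS is analyzed as an efficacy variable in SAP 8.3.4, with descriptive statistics by arm and visit and this count: "The number and percentage of subjects with scores <8 for the HADS-A and HADS-D will be summarized by treatment group at each visit".

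Protocol 6.3 attaches actions to these instruments. Criterion 8a requires withdrawal for a positive C-SSRS Question 4 or 5 or suicidal behavior. Criterion 9a requires withdrawal for HADS-D of 15 or more and referral for HADS-D above 10. Both criteria are among those that lead to DMC referral under Protocol 6.4 once more than one subject meets any of them.

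**The concern.** Two things do not fit together. First, the SAP promises a table that includes anxiety and then specifies a search whose title does not mention it, while its own lists omit the topic. A programmer working from the text cannot tell whether anxiety belongs in the table or which terms would bring it in.

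Second, the protocol defines these topics by instrument and sets numerical action points on them, yet the special-monitoring table draws only on coded treatment-emergent adverse events (TEAEs), and no other summary counts subjects past those points.

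At stake is whether the study report can be read correctly on neuropsychiatric safety. An empty or near-empty special-monitoring table would look reassuring, although subjects might have crossed thresholds that the protocol treats as grounds for referral or withdrawal.

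**Working it through.** The plan states no figure on this point, so the check sets the sections side by side.

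**Step 1: stated scope against stated search.**

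| Place | Depression | Suicidality | Anxiety |
|---|---|---|---|
| Protocol 12.1.3 | yes | yes | yes |
| SAP 14.6.5, scope sentence | yes | yes | yes |
| SAP 14.6.5, title of the only query | yes | yes | not named |
| SAP 11.2.3 and 14.6, topic lists | yes | yes | not named |

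Anxiety is in two of the four rows. No row gives a rule for retrieving it.

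**Step 2: where an anxiety TEAE would appear.** It is counted in the general tables of SAP 11.2.3 (for example "Incidence of TEAEs Overall"), by system organ class, high level term and preferred term. One of those tables carries exposure-adjusted incidence and event rates. What may be lost is its contribution to the grouped neuropsychiatric count and to that table's own exposure-adjusted rates.

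**Step 3: what is counted at the protocol's thresholds.**

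| Threshold (Protocol 6.3) | Planned output | Count at the threshold? |
|---|---|---|
| C-SSRS Question 4 or 5, or behavior | Listing (SAP 11.4.4.3) | No |
| HADS-D above 10 | Descriptive statistics; number below 8 (SAP 8.3.4) | No |
| HADS-D 15 or more | Same | No |

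The number below 8 gives the number at 8 or more among observed subjects, which mixes scores of 8 to 10 with the action range. The maximum in the descriptive statistics shows whether a visit had a score of 15 or more, but not how many subjects did.

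**Step 4: can an instrument finding reach the special-monitoring table?** Only if the investigator records it as an adverse event that codes to a term in the query. The definition in Protocol 12.1.1 is broad enough to allow this. Where the protocol wants a finding recorded as an adverse event, it says so: potential drug-induced liver injury in 12.5.1 and significant physical examination changes in 12.6.5. There is no matching instruction for HADS in 9.4, for the C-SSRS in 12.6.7, or in criteria 8a and 9a.

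**Step 5: how the SAP treats comparable topics.** Hepatic events get a query (14.6.8) and a separate table of subjects passing liver-test thresholds (11.3, 14.5). Laboratory values, vital signs and QTcF also get threshold counts (11.3, 11.4.1, 11.4.3).

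**Step 6: weight of one case.** With the planned numbers, one subject is 1/30 = 3.3% of arm A, 1/15 = 6.7% of arm B and 1/45 = 2.2% overall. Two subjects (2/45 = 4.4%) are enough for DMC referral under Protocol 6.4. Exclusion criterion 29a bars HADS-D above 10 at entry, so a post-Baseline value above 10 is, apart from eligibility deviations, a newly reached one.

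**The case against.** The best case for the plan is that little is actually hidden. The query is run in broad and narrow scope, and its terms cannot be seen here, so it may retrieve some anxiety terms. The topic lists introduce depression and suicide as particular examples, which is not a strict exclusion of anxiety. Naming an instrument in Protocol 12.1.3 says how a topic is assessed, not that every score must enter a coded-event table. A neuropsychiatric adjudication committee reviews potential suicide events, and DMC outputs are set out in a separate DMC SAP (SAP 4.5.1), which may contain threshold counts. In an exploratory study of about 45 subjects, listing rare C-SSRS positives is common practice.

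Most of this stands, and it rules out stronger readings. A reader might infer that anxiety events and instrument-detected cases are never counted. The documents do not support that: anxiety TEAEs are in the general tables, HADS scores are summarized by visit with early-withdrawal values mapped in (SAP 4.4), C-SSRS results are listed, and a recorded and coded case can enter the special-monitoring table.

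A reader might also infer that HADS percentages conceal withdrawals, because "The percentages will be based on the number of available observations at each visit". The same sentence commits to tabulating the number with missing data, so the loss is visible. Scoring missing HADS values as abnormal would be a poor remedy, since subjects leaving for the extension study after a PASI relapse would be counted as psychiatrically abnormal.

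What the objection does not answer is the mismatch within the SAP over anxiety, or the absence of any threshold count among the outputs that this SAP defines for the study report.

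**Conclusion.** The point holds as a gap in specification. As written, SAP 14.6.5 does not reliably deliver its stated scope: anxiety events may be missing from the neuropsychiatric table and its exposure-adjusted rates, and threshold cases not recorded as adverse events will be outside it. No summary in the SAP counts subjects meeting the C-SSRS or HADS-D thresholds of Protocol 6.3.

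The number of events affected cannot be estimated from the documents. In a study this small, one or two subjects could be the whole signal. No efficacy result or sample-size figure depends on this.

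Two assumptions carry the conclusion. The query's content is judged by its title. It is also assumed that the CRF completion guidelines, which are not available here, do not require every threshold finding to be recorded as an adverse event. If the query does include anxiety terms, the inconsistency between SAP sections and the missing threshold counts remain. If the guidelines do require recording, fewer cases would be missed, but there would still be no threshold count.

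**What to change.** 1. Align the topic descriptions in SAP 11.2.3, 14.6 and 14.6.5 with Protocol 12.1.3, so that all name depression, anxiety and suicidal ideation or behavior.
2. In SAP 14.6.5, add a MedDRA anxiety term group to the existing query and fix its terms before unblinding.
3. Add one table to the special-monitoring outputs, by arm and for All Subjects, giving the number and percentage of subjects who at any post-Baseline visit meet each existing threshold: C-SSRS Question 4 or 5 or suicidal behavior; HADS-D above 10; HADS-D of 15 or more. State that early-withdrawal and unscheduled assessments count. SAP 4.3 allows unscheduled data in abnormality tables only where the SAP says so, and Protocol 8.13 calls for a C-SSRS at unscheduled visits made for safety or efficacy reasons.

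The All Subjects column must be stated explicitly, because Table 14-1 does not provide it for safety data other than adverse events.

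The cost is one extra search group, one table and some SAP wording. The data are already collected, and no visit, procedure, threshold or withdrawal rule changes.

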14.6.6 Inflammatory bowel disease

Inflammatory bowel disease events will be tabulated separately, based on the HLT = ‘Colitis excl infective’.

14.6.7 Anaphylactic reaction

Anaphylactic reactions will be summarized together in a stand-alone table with the following incidence rows:

- The first row within the body of the table will be labeled ‘Any hypersensitivity/anaphylactic reaction’ and will represent the overall incidence of subjects who reported at least one hypersensitivity reaction or at least one anaphylactic reaction.
- The second row within the body of the table will be labeled ‘Any hypersensitivity reaction’ and will represent the overall incidence of subjects who reported at least one hypersensitivity reaction.
- The third row within the body of the table will be labeled ‘Any anaphylactic reaction’ and will represent the overall incidence of subjects who reported at least one anaphylactic reaction.

Following these three overall incidence rows, all TEAEs that have been identified as either a hypersensitivity reaction or an anaphylactic reaction will be summarized by SOC, HLT and PT (these will not be presented by subcategory).

Hypersensitivity reactions and anaphylactic reactions will be identified as follows:

- **Hypersensitivity reactions:** all TEAEs with onset (start date/time) within 24 hours after any administration of IMP, which code to a PT which contains the term ‘hypersensitivity’ will be considered to be a hypersensitivity reaction and included in the summary table
- **Anaphylactic reactions:** An algorithmic approach will be used to identify TEAEs that are considered to be anaphylactic reactions. Preferred terms are separated into 4 distinct categories (A, B, C, D) prior to the algorithmic approach being applied.

All TEAEs with onset (start date/time) within 24 hours after any administration of IMP, and which fulfill any of the 3 criteria described in [Section 14.6.7.1](#) will be included in the summary table.

Any TEAEs with missing start time will be assumed to have occurred at the time of or after dosing for this purpose, if the event date is on the same day as a dosing date.

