**Table 12–3: Required investigations and follow up for PDILI**

Laboratory value		Symptoms a of hepatitis of hypersensitivity	Immediate		Follow up	
ALT or AST	Total bilirubin		Consultation requirements	Actions	Testing	Evaluation

ALT=alanine aminotransferase; ASAP=as soon as possible; AST=aspartate aminotransferase; HCP=healthcare practitioner; IMP=investigational medicinal product; NA=not applicable; PDILI=potential drug-induced liver injury; ULN=upper limit of normal

a Hepatitis symptoms include fatigue, nausea, vomiting, and right upper quadrant pain or tenderness; hypersensitivity symptoms include eosinophilia (>5%), rash, and fever (without clear alternative cause).

b If the subject also has  $\geq 2 \times$ ULN ALP, the possibility of an indication of biliary obstruction should be discussed with the Medical Monitor.

c Details provided in [Section 12.5.1.1](#). The local hepatologist is the expert usually consulted by the treating physician for assessment and management of potential hepatic disease. This would usually be a hepatologist, but may be a gastroenterologist.

d Unless an alternative monitoring schedule is agreed by the investigator and UCB responsible physician. Determination of stabilization is at the discretion of the investigator in consultation with the hepatologist (as applicable) and UCB responsible physician, as needed.

This document cannot be used to support any marketing authorization application and any extensions of any marketing authorization

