14.6.7.1 Anaphylactic reaction algorithm

The SMQ = ‘anaphylactic reaction’ consists of 3 parts:

- A **narrow search** containing PTs that represent core anaphylactic reaction terms. If a subject reports any TEAE which codes to a PT included in Category A, then the event will be flagged as an anaphylactic reaction and summarized as such in the table.

– Category A

1. Anaphylactic reaction
2. Anaphylactic shock
3. Anaphylactic transfusion reaction
4. Anaphylactoid reaction
5. Anaphylactoid shock
6. Circulatory collapse
7. Dialysis membrane reaction
8. Kounis syndrome
9. Shock
10. Shock symptom
11. Type I hypersensitivity

- A **broad search:** If a subject reports any TEAE which codes to a PT included in Category B **AND** reports any TEAE which codes to a PT included in Category C, **and both TEAEs have the same start date**, then both events will be flagged as anaphylactic reactions and summarized as such in the table.

– Category B

1. Acute respiratory failure
2. Asthma
3. Bronchial oedema

4. Bronchospasm
5. Cardio-respiratory distress
6. Chest discomfort
7. Choking
8. Choking sensation
9. Circumoral oedema
10. Cough
11. Cyanosis
12. Dyspnoea
13. Hyperventilation
14. Irregular breathing
15. Laryngeal dyspnoea
16. Laryngeal oedema
17. Laryngospasm
18. Laryngotracheal oedema
19. Mouth swelling
20. Nasal obstruction
21. Oedema mouth
22. Oropharyngeal spasm
23. Oropharyngeal swelling
24. Respiratory arrest
25. Respiratory distress
26. Respiratory dyskinesia
27. Respiratory failure
28. Reversible airways obstruction
29. Sensation of foreign body
30. Sneezing
31. Stridor
32. Swollen tongue
33. Tachypnoea
34. Throat tightness
35. Tongue oedema
36. Tracheal obstruction

-
- 37. Tracheal oedema
 - 38. Upper airway obstruction
 - 39. Wheezing

– **Category C**

- 1. Allergic oedema
- 2. Angioedema
- 3. Erythema
- 4. Eye oedema
- 5. Eye pruritis
- 6. Eye swelling
- 7. Eyelid oedema
- 8. Face oedema
- 9. Flushing
- 10. Generalised erythema
- 11. Injection site urticaria
- 12. Lip oedema
- 13. Lip swelling
- 14. Nodular rash
- 15. Ocular hyperaemia
- 16. Oedema
- 17. Periorbital oedema
- 18. Pruritis
- 19. Pruritis allergic
- 20. Pruritis generalised
- 21. Rash
- 22. Rash erythematous
- 23. Rash generalized
- 24. Rash pruritic
- 25. Skin swelling
- 26. Swelling
- 27. Swelling face
- 28. Urticaria

29. Urticaria papular

– **Category D**

1. Blood pressure decreased
2. Blood pressure diastolic decreased
3. Blood pressure systolic decreased
4. Cardiac arrest

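### The SAP's hypersensitivity/anaphylaxis table leaves out isolated urticaria or angioedema and any reaction starting more than 24 hours after a dose, so it can understate the protocol's hypersensitivity topic

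*SAP*

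**What the plan says.** Protocol 12.1.3 lists the AESM topics. The list includes "cytopenias, hypersensitivities, suicide ideation or behavior (assessed using the C-SSRS", and sets no time limit and no coding rule for hypersensitivities.

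SAP 11.2.3 and 14.6 take the topic up in a combined entry, "Anaphylactic reaction (hypersensitivity and anaphylactic reactions", and promise both an exposure-adjusted incidence rate (EAIR) and an exposure-adjusted event rate (EAER) for every AESM table. SAP 14.6.7 then defines the two kinds of event:

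- **Hypersensitivity reaction:** "all TEAEs with onset (start date/time) within 24 hours after any administration of IMP, which code to a PT which contains the term" 'hypersensitivity'.
- **Anaphylactic reaction:** "All TEAEs with onset (start date/time) within 24 hours after any administration of IMP, and which fulfill any of the 3 criteria" set out in 14.6.7.1.

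Under 14.6.7.1 a Category A term counts alone. Urticaria and angioedema are in Category C. The broad search begins "If a subject reports any TEAE which codes to a PT included in Category B" and needs a Category C event as well, with the condition "and both TEAEs have the same start date". The third criterion pairs a Category D event with a Category B or C event under the same date condition.

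One rule loosens the window for events on a dosing date: "Any TEAEs with missing start time will be assumed to have occurred at the time of or after dosing for this purpose".

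**The concern.** An AESM table exists so that a reader need not assemble a named risk from scattered preferred terms. Here the word match and the 24-hour window act together, and each removes a plausible kind of reaction. The word match drops urticaria or angioedema occurring alone, even two hours after the injection. The window drops anything later, even when the term names hypersensitivity outright. The row could then read zero although allergic reactions occurred.

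The product is a subcutaneous antibody. Protocol 2.2.1 gives a half-life of about 28 days, and anti-drug antibodies are a primary variable, so reactions beyond the first day cannot be dismissed in advance. What is at stake is how far one descriptive safety table, and the rates printed in it, can be taken at their label.

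**Working it through.** The documents give no figure to reproduce. The check applies the rules to example cases and then compares the countable time with the time at risk.

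**Step 1. Apply SAP 14.6.7 and 14.6.7.1 to example cases.**

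| Case | Hypersensitivity row | Anaphylactic row |
|---|---|---|
| Urticaria alone, 2 h after dose | no | no |
| Angioedema alone, 2 h | no | no |
| Urticaria and angioedema, same day, 2 h | no | no (both Category C) |
| Urticaria and wheezing, same day, 2 h | no | yes (C with B) |
| Hypotension and urticaria, same day, 2 h | no | yes (D with C) |
| 'Drug hypersensitivity', 2 h | yes | no |
| 'Drug hypersensitivity', 48 h | no | no |
| 'Anaphylactic reaction', 48 h | no | no |

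Category C holds 29 terms. None contains the word 'hypersensitivity', so none counts alone.

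**Step 2. Countable time against time at risk.** Inputs:

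- Dosing visits: Baseline, Week 4 and Week 16 (SAP 11.1.1), giving three 24-hour windows, or 3 days.
- Time at risk with full follow-up (SAP 11.1.3, formula 11): (last dose − first dose) + 140.
- Time at risk on entering the extension study (formula 12): (last contact − first dose) + 1.

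All doses on schedule and full follow-up: 16 × 7 + 140 = 112 + 140 = 252 days, so 3/252 = 1.2%.

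Entry to the extension at Week 20: 20 × 7 + 1 = 141 days, so 3/141 = 2.1%.

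In arm A the Week 16 injection is placebo, so only two of the three windows follow bimekizumab: 2/252 = 0.8%.

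**Step 3. Effect on the rates.** SAP 11.2.2 gives EAIR = 100 × n / ΣT and EAER = 100 × (number of events) / ΣT. For the EAIR, a subject without the event contributes the whole time at risk. For the EAER, every subject does. An on-schedule completer without an event adds 252/365.25 = 0.69 years to the denominator, while an event can reach the numerator only during 3/365.25 = 0.008 of those years. Numerator and denominator therefore cover different periods.

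**Step 4. Compare the other AESM definitions in SAP 14.6.** Of the seven other topics, five use standardized MedDRA queries: major cardiovascular events, malignancies, cytopenias, neuropsychiatric events and hepatic events. None of the seven has a window tied to dosing. Only the hypersensitivity row is found by matching a word.

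**The case against.** Several points on the other side stand.

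- **The events are not lost.** A reader might infer that they go unreported. Every TEAE up to 140 days after the last dose appears in the tables by system organ class and preferred term, one of which carries EAIR and EAER (SAP 11.2.1 and 11.2.3). The AE listings give days since the most recent dose. With about 45 subjects, a case of urticaria can be found.
- **The protocol is not contradicted.** It names a topic for monitoring and promises no search, window or table. Section 14 leaves statistical detail to the SAP. A narrow, reproducible rule is a legitimate choice in principle, and specificity matters where skin complaints are common background.
- **The rates are not miscalculated.** They are correct for the event as defined, but that event is narrower than the row label.
- **The 1.2% is not the share of reactions missed.** The documents give no distribution of onset times, and reactions may cluster near dosing.
- **The liver section does not define the topic.** Protocol Table 12–3 says that "hypersensitivity symptoms include eosinophilia (>5%), rash, and fever (without clear alternative cause", but this describes symptoms accompanying raised ALT or AST. It does not set the AESM definition.
- **Recording practice may help.** Protocol 12.1.5 asks for a diagnosis in place of separate symptoms, so some reactions presenting as hives may be coded to a hypersensitivity term. Urticaria can itself be the diagnosis, however, so the gap remains.

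These points limit the consequence. They do not change how the cases in Step 1 are classified.

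**Conclusion.** The concern holds for one table. The AESM rows for hypersensitivity and anaphylaxis omit isolated urticaria, angioedema, allergic oedema and injection site urticaria, and omit reactions starting after 24 hours. The one softening is that a dosing-day event with no recorded time is taken as occurring at or after the dose. The row and its rates can therefore understate the topic the protocol names. How many reactions this would remove cannot be estimated from the documents.

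The 252-day figure assumes all three doses on schedule and follow-up to 140 days after the last. It falls to 141 days for a subject entering the extension at Week 20.

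This is an inexpensive improvement to a descriptive safety output. Safety is a secondary objective, the study is not powered for it, no stopping rule uses this row, and the primary endpoint is unaffected.

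**What to change.** In SAP 14.6.7, define 'Any hypersensitivity reaction' as any TEAE whose preferred term contains 'hypersensitivity' or is one of five terms already in Category C: Urticaria, Urticaria papular, Angioedema, Allergic oedema and Injection site urticaria. Count it over the full TEAE period, so that numerator and denominator cover the same time. Keep onset within 24 hours of an IMP administration as a sub-row, with a footnote that any rate shown there still uses full follow-up. Leave the anaphylaxis algorithm, including its window, unchanged. Nonspecific terms such as Rash, Erythema and the pruritus terms stay out.

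A standardized MedDRA hypersensitivity query would match the approach used for most other topics. Its content is not in the documents, so its coverage and specificity cannot be judged here. The five-term addition can be judged from the SAP alone.

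The cost is one extra flag and one extra row, with no new data. The downside is that some urticaria or similar events unrelated to drug will be counted; the 24-hour sub-row helps a reader separate them. SAP section 1 gives the route: a further SAP amendment before database lock or, after lock, a supplementary analysis described with its rationale in the study report.
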